6.2. Exclusion Criteria

Patients will be excluded from study enrollment if they meet any of the following criteria at screening:

Medical Conditions

[16] Have any other condition (including known drug or alcohol abuse or psychiatric disorder including eating disorder) that precludes the patient from following and completing the protocol

[17] Have hypoglycemia unawareness as judged by the investigator

[18] Have had more than 1 episode of severe hypoglycemia (defined as requiring assistance due to neurologically disabling hypoglycemia) within 6 months prior to screening

[19] Have had more than 1 emergency room visit or hospitalization due to poor glucose control (hyperglycemia or DKA) within 6 months prior to screening

[20] Have cardiovascular disease, within the last 6 months prior to screening, defined as stroke, decompensated heart failure New York Heart Association class III or IV (CCNYHA 1994), myocardial infarction, unstable angina pectoris, percutaneous transluminal coronary angioplasty or coronary arterial bypass graft

[21] Renal:

- a. History of renal transplantation
- b. Currently receiving renal dialysis
- c. Serum creatinine >2.0 mg/dL (177 µmol/L) at screening, or
- d. An estimated glomerular filtration rate of <30 mL/min/1.73 m².

[22] Hepatic: have obvious clinical signs or symptoms of liver disease (for example, acute or chronic hepatitis, or cirrhosis), or elevated liver enzyme measurements as indicated below at screening:

- a. Total bilirubin level (TBL) $\geq 2X$ the upper limit of normal (ULN) (with the exception of Gilberts Disease) as defined by the central laboratory,

Or

- b. Alanine aminotransferase (ALT) $\geq 3X$ ULN as defined by the central laboratory,

Or

- c. Aspartate aminotransferase (AST) $\geq 3X$ ULN as defined by the central laboratory

[23] Malignancy: have active or untreated malignancy, have been in remission from clinically significant malignancy (other than basal cell or squamous cell skin cancer) for less than 5 years, or are at an increased risk for developing cancer or a recurrence of cancer in the opinion of the investigator

[24] Have any hypersensitivity or allergy to any of the insulins or excipients used in this trial

[25] Hematologic: have had a blood transfusion or severe blood loss within 90 days prior to screening or have known hemoglobinopathy, anemia that is clinically significant based on investigator judgement, or any other traits of known to interfere with measurement of HbA1c

[26] Have presence of clinically significant gastrointestinal disease (for example, clinically active gastroparesis associated with wide glucose fluctuations; includes those with gastric bypass) in the opinion of investigator

[27] Have significant lipohypertrophy, lipoatrophy, or scars within the SC tissue in areas of infusion, in the opinion of the investigator

[28] Have a history of abscess at an infusion site within the last 90 days prior to screening

[29] Have vision loss or hearing loss that does not allow recognition of pump screens, alerts and alarms

Prior/Concomitant Therapy

[30] Have used insulin human inhalation powder (Afrezza®) within 30 days prior to screening

[31] Are receiving any oral or injectable medication intended for the treatment of diabetes other than rapid-acting analog insulin via CSII in the 90 days prior to screening. In the event of interruption of CSII ≤ 14 days during the 6 months prior to screening, injection of bolus and basal insulin is allowed.

- [32] Glucocorticoid therapy: are receiving chronic (lasting longer than 14 consecutive days) systemic glucocorticoid therapy (including intravenous (IV), intramuscular (IM), SC, and oral), but excluding topical, intraocular, intranasal, intra-articular, and inhaled preparations), or have received such therapy within 4 weeks immediately prior to screening with the exception of replacement therapy for adrenal insufficiency

Prior/Concurrent Clinical Trial Experience

- [33] Are currently enrolled in any other clinical trial involving an IP or any other type of medical research judged not to be scientifically or medically compatible with this study
- [34] Have participated, within the last 30 days in a clinical trial involving an IP
- [35] Have previously completed or withdrawn from this study or any other study investigating LY900014 after receiving at least 1 dose of the IP

Other Exclusions

- [36] Have an irregular sleep/wake cycle (for example, patients who sleep during the day and work during the night)
- [37] Are investigator site personnel directly affiliated with this study and/or their immediate families. Immediate family is defined as a spouse, parent, child, or sibling, whether biological or legally adopted
- [38] Are Lilly employees (including employees, temporary contract workers, or designees responsible for the conduct of the study)

6.2.1. Rationale for Exclusion of Certain Study Candidates

The use of LY900014 in pediatric patients (<18 years of age) will be studied separately. This study will specifically examine comparison of LY900014 to Humalog in adult patients using CSII. Criterion [2] defines the population age for the purpose of this study. Therefore, pediatric patients are excluded.

6.3. Lifestyle Restrictions

Patients should be instructed not to donate blood or blood products during the study. Patients should be instructed to avoid major changes in diet or exercise during the study. Patients should be instructed to avoid all medications that contain acetaminophen/paracetamol during the blinded CGM study sessions. Patients should be instructed to avoid major changes in dietary intake or physical activity during the 3 days prior to mixed meal tolerance test (MMTT).

6.4. Screen Failures

Individuals who do not meet the criteria for participation in this study (screen failure) may not be rescreened, with the exception of individuals from select countries who initially screen failed because they use a Paradigm Revel or Paradigm Veo pump. Retests are also not allowed, except for cases when results are unavailable from the original sample.

7. Treatments

7.1. Treatments Administered

This study involves a double-blind comparison of LY900014 and Humalog, in patients with T1D using CSII. [Table ITRO.3](#) shows the treatment regimens.

Table ITRO.3. Treatment Regimens

Regimen	Dose Strength	Dose Administration	Route of Administration	Timing of Dose
LY900014	100 U/mL	Individualized Dosing	CSII	Mealtime bolus 0-2 min prior to start of the meal; continuous basal infusion; correction boluses as necessary
Humalog	100 U/mL	Individualized Dosing	CSII	Mealtime bolus 0-2 min prior to start of the meal; continuous basal infusion; correction boluses as necessary

Abbreviation: CSII = continuous subcutaneous insulin infusion.

The investigator or his or her designee is responsible for the following:

- explaining the correct use of IP to the patient
- explaining storage requirements for IP
- explaining requirements for recording time and amount of bolus doses to the patient
- maintaining accurate records of IP dispensing and collection
- at the end of the study returning all used and unused IP to Lilly, or its designee, unless the sponsor and sites have agreed all unused medication is to be destroyed by the site, as allowed by local law

7.1.1. Packaging and Labelling

Clinical trial materials will be labeled as IP as appropriate, and according to the regulatory requirements of the country. Study insulins (LY900014 and Humalog) will be supplied by Lilly or its representative, in accordance with current good manufacturing practices and will be supplied with lot numbers.

The blinded vials will contain a concentration of 100 U/mL in 10-mL vials of either LY900014 or Humalog.

During the lead-in period, Humalog 100 U/mL will be provided in open-label 10-mL vials.

7.1.2. Insulin Pumps

Patients will use their personal insulin pumps for the duration of the study but will be required to use reservoirs and infusion sets provided by the investigative site. Pump reservoirs will be filled

with IP and infusion sets will be primed according to the manual of use provided by the pump manufacturer. Patients will be required to change the insulin, reservoir, and infusion set every 3 days, routinely throughout the study, in accordance with the label of the infusion sets. Sites should assist patients with setting a reminder in their pump to prompt for a reservoir and infusion set change every 3 days.

If a pump malfunction requires a patient to change to a new insulin pump during the study, it will be allowed as long as the new pump

- is approved in the country where the patient resides
- is allowed by the study (MiniMed 530G, Paradigm Revel, 630G, Paradigm Veo or 640G)
- Training has been provided to the patient by a qualified HCP, and
- is compatible with a Contour Link blood glucose meter that
 - is approved in the country where the patient resides and
 - can be sourced by the Sponsor for the Study.

7.1.2.1. Personal Continuous Glucose Monitor Use in Study

Patients may continue to use their personal CGM or FGM during the study.

Patients will not be allowed to start using personal CGM or FGM during the study. In order to account for potential differences between patients who wear a CGM or FGM and those who do not, stratification by patients' personal CGM or FGM use will ensure balance of this factor across treatments. Patients may use their personal CGM or FGM for the required glucose value entries into the pump bolus calculator for meal and correction boluses, if approved in their country for making treatment decisions (i.e., nonadjunctive use). Patients will be required to perform SMBG with the study provided blood glucose meter for the study procedures described in Section 9.1.4.3.

7.1.3. Medical Devices

Study patients will be provided with an approved, compatible blood glucose meter. The patient's meter must be wirelessly connected to their insulin pump. Instructions for connecting are found in the pump and meter user guides and also provided as a site tool. Once connected, the pump automatically controls the date and time of the meter. It will also send all BG results directly to the pump when the "Always" meter send option is selected (recommended). The BG meters used in this study will be have received clearance from the Food and Drug Administration (FDA) and meet the following standard for blood glucose meters: ISO 15197:2013. At every site visit beginning with Visit 2, site staff should verify synchronization of the dates and times of the pump and BG meter.

7.2. Method of Treatment Assignment

Patients who meet all criteria for enrollment will be randomized to double-blind treatment at Visit 4. Assignment to treatment groups will be determined by a computer-generated random sequence using an interactive web-response system (IWRS). The IWRS will be used to assign all vials containing double-blind IP during the study and open-label Humalog during the lead-in

period. Site personnel will confirm that they have located the correct vials by entering a confirmation number found on the vials into the IWRS.

Patients will be randomized to 1 of 2 treatment groups in 1:1 ratio. Stratification will be by country, HbA1c stratum ($\leq 7.5\%$, $> 7.5\%$ at Visit 1), and patient's personal CGM or FGM use during the study (yes/no).

Patients will begin using double-blind IP in their pumps immediately following successful completion of the Visit 4 MMTT. Patients will fill a new pump reservoir and infusion set with IP, then insert a new pump infusion set cannula and begin infusion of IP prior to leaving the investigative site.

7.2.1. Selection and Timing of Doses

7.2.1.1. Target Glucose Values for Titration of Insulin Therapy

The overall glycemic control goals for all patients enrolled in the study are similar to those recommended by the American Association of Clinical Endocrinologists (AACE) (Bailey et al. 2016). Fasting, prandial, bedtime, and peak PPG target values used to reach the glucose targets and for determination of titration in insulin therapy are listed in [Table ITRO.4](#)

Table ITRO.4. Target Glucose Values for Titration of Insulin Therapy

Time of Measurement	Target (Range)
Fasting or pre-morning meal	Target: 100 mg/dL or 5.6 mmol/L Range: 80 to <100 mg/dL or 4.4 to 6.1 mmol/L
Pre-midday meal	Target: 100 mg/dL or 5.6 mmol/L Range: 80 to <110 mg/dL or 4.4 to 6.1 mmol/L
Pre-evening meal	Target: 100 mg/dL or 5.6 mmol/L Range: 80 to <110 mg/dL or 4.4 to 6.1 mmol/L
Pre-bedtime and 03:00 AM	Range: 90 to 130 mg/dL or 5.0 to 7.2 mmol/L
1-2-hour postprandial	Target: <180 mg/dL or 10.0 mmol/L

7.2.1.2. Pump Settings

Evaluating and titrating pump settings is at the discretion of the investigator and should be done with a methodical approach by reviewing relevant glucose data, insulin delivery settings and carbohydrate intake. During titration of pump settings, patients should eat meals that have known carbohydrate content and can be accurately counted and avoid snacking between meals (unless treating hypoglycemia). Patients will be allowed to use low glucose suspend for the lead-in and duration of the treatment period. Patients will not be allowed to use “SmartGuard Suspend before low” (Refer Section [6.1](#) Inclusion Criteria [12]).

7.2.1.3. Basal Rate Titration

At all clinic and telephone visits during the 16-week treatment period following randomization, titration of basal rates should be based on glucose values, hypoglycemia data and determined by the investigator in discussion with the patient. Additional discussion between visits may be

required to enable the patient to reach the fasting blood glucose target of 100 mg/dL (5.6 mmol/L) and to optimize 24-hour basal rates. Titration of basal rates may be influenced by other clinical circumstances and safety considerations known to the investigator; thus, the prescribed basal rates during the study are determined by, and the responsibility of, the investigator.

Overnight basal rates should be assessed by observing patterns across time segments (bedtime to mid-sleep; mid-sleep to awakening) and titrated to match diurnal variations. When basal rates are set correctly, patients should be able to sleep late, eat late, or skip a meal without experiencing glucose excursions.

Daytime basal rates can be titrated using either the fasting method or nonfasting method.

If using the fasting method, evaluate glucose levels across skipped-meal time segments (pre-morning to pre-midday, pre-midday to pre-evening, or pre-evening to bedtime) and titrate/add basal rate(s) based on the patterns observed across skipped-meal times.

If using the nonfasting method, evaluate basal rates by comparing the 2-hour postmeal glucose to the next premeal glucose. Postmeal glucose should steadily decline and return to premeal target range by next meal.

7.2.1.4. Bolus Dose Titration

Postprandial glucose levels from 10-point SMBG profiles and 7-point glucose profiles should be evaluated by the investigator for titration of bolus dosing. Additional glucose testing should be considered during the days following transition to study insulin. Titration of bolus calculator settings (CR, ISF, and AIT) during the study are determined by, and the responsibility of, the investigator.

Patients should use the pump Bolus Wizard® calculator for calculating bolus and correction doses to ensure that the carbohydrate content of each meal is covered and the preprandial glucose level is accounted for in the preprandial bolus dose.

In order to meet the target glucose levels during the 16-week treatment period, the investigator in discussion with the patient should;

- Weekly assess and titrate the CR, ISF, and AIT
 - The CR is used to calculate food bolus amounts. Evaluate CRs by comparing the pre-meal glucose to its corresponding 2-hour post-meal glucose. The CR may be titrated every 3-4 days (twice per week) when appropriate, based on the patient's glycemic needs and glucose levels.
 - The ISF is used to calculate correction bolus amounts that is needed to bring the glucose into target range.

- Weekly discuss and determine optimal bolus types (normal, square or dual wave) for meals of different macronutrient composition. For meals that tend to be larger in size and of higher protein and fat content (often the dinner meal), a higher bolus dose or a dual or square wave bolus may be appropriate to prevent late postmeal hyperglycemia.

7.2.1.5. Transitioning off Study Prandial Insulin Therapy

Patients will give their last bolus dose of study insulin (LY900014 or Humalog) at Visit 13 with the MMTT or at early discontinuation. No special instructions are necessary for patients who were randomized to either LY900014 or Humalog. After completion of study treatment, patients will restart the rapid-acting insulin analog used prior to study entry via CSII and their pumps settings will be reset to those used at randomization.

7.3. Blinding

This is a double-blind study. LY900014 and Humalog treatment groups will have premeal bolus doses given via CSII. Investigators, patients, and study site personnel will be blinded to assigned dosing regimens throughout the study.

To preserve the blinding of the study, the Lilly study team will remain blinded throughout the study; only a minimum number of Lilly personnel will see the randomization table and treatment assignments before the study is complete.

Emergency unblinding for AEs may be performed through the IWRS. This option may be used ONLY if the patient's well-being requires knowledge of the patient's treatment assignment. Unblinding events are recorded and reported by the IWRS.

If an investigator, site personnel performing assessments, or patient is unblinded, the patient must be discontinued from IP and should remain in the study.

In case of an emergency, the investigator has the sole responsibility for determining if unblinding of a patient's treatment assignment is warranted. Patient safety must always be the first consideration in making such a determination. If the investigator decides that unblinding is warranted, the investigator should make every effort to contact the Lilly clinical research physician/clinical research scientist (CRP/CRS) prior to unblinding a patient's treatment assignment unless this could delay emergency treatment of the patient. If a patient's treatment assignment is unblinded, Lilly must be notified immediately.

7.4. Dosage Modification

See Section [7.2.1](#).

7.5. Preparation/Handling/Storage/Accountability

The investigator or his or her designee is responsible for confirming appropriate temperature conditions have been maintained during transit for all study treatment received and any discrepancies are reported and resolved before use of the study treatment.

Only participants enrolled in the study may receive IP, and only authorized site staff may supply or administer study treatment. All study treatments should be stored in an environmentally controlled and monitored (manual or automated) area in accordance with the labeled storage conditions with access limited to the investigator and authorized site staff.

All insulin products must be stored at the investigative site under refrigerated conditions (between 2°C and 8°C) in a locked and secure place. Insulin must not be frozen.

Vials of insulin not currently in-use should be refrigerated until ready to use. In-use insulins should be maintained at room temperature (between 20°C and 25°C) when possible and refrigerated material should be warmed to near room temperature before infusion. In-use insulin must not be used after 28 days.

The investigator is responsible for study treatment accountability, reconciliation, and record maintenance (such as receipt, reconciliation, and final disposition records).

7.6. Treatment Compliance

The investigator or designee will assess compliance of the patient at each visit, based on a review of the patient's glycemic control, adherence to the visit and treatment schedule, and completion of the patient's study diary. Patients who are deemed noncompliant will receive additional diabetes education and training, as required, and the importance of compliance with the protocol will be reinforced. Patients who, in the opinion of the investigator, are deemed consistently noncompliant may be discontinued from IP.

7.7. Concomitant Therapy

The following concomitant medications

- are NOT allowed at any time during the study;
 - Any noninsulin diabetes treatment therapy
 - AfreZZA® (inhaled insulin)
- Are NOT allowed during the blinded CGM sessions;
 - Medicines containing Acetaminophen/paracetamol
- ARE allowed for up to a total of 7 days during the lead-in period and 14 days during the treatment period;
 - Systemic glucocorticosteroids
 - IV, IM, SC, oral
 - except in the case of replacement therapy for adrenal insufficiency
- ARE allowed for 14 days or less during the study
 - Basal insulin

- Regular human insulin or a nonstudy rapid-acting analog insulin
- ARE allowed at any time
 - Topical, inhaled, intraocular, intra-articular, or intranasal steroid preparations

7.8. Treatment after the End of the Study

7.8.1. Treatment after Study Completion

LY900014 will not be made available to patients after conclusion of the study. Rapid-acting insulin analogs and regular human insulin are available in all countries for use as prandial/pump insulin.

7.8.2. Special Treatment Considerations

After discontinuation of IP at the end of the treatment period or earlier, randomized patients should restart the rapid-acting analog insulin used prior to study entry.

Investigators should provide patients with appropriate guidance for glucose monitoring and insulin dose adjustment throughout the follow-up period in order to maintain glycemic control.

8. Discontinuation Criteria

8.1. Discontinuation from Study Treatment

In the event that a patient is discontinued from the study treatment, the investigator should encourage the patient to remain in the study for continued safety monitoring.

Lilly recognizes the importance of complete data collection. This study includes elements to minimize missing data. Patients who are discontinued from IP before study completion are encouraged to remain in the study for continued monitoring. For patients who remain in the study after early discontinuation of IP, both efficacy (HbA1c) and safety data will be collected at scheduled visits. The difference between stopping IP and discontinuing the study will be explained to patients as part of the informed consent, and patients will be encouraged to continue in the study even if they stop study drug. In addition, study site investigators will be trained on the importance of complete data collection, with additional re-education of sites and patients as necessary.

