5.2. Number of Participants

Numbers are approximate: 526 participants will be screened to achieve 420 randomized and 368 patients completing 16 weeks of treatment.

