5.3.1. Safety Follow-up

Safety follow-up visit guidelines are as follows (see Section 2, [Table ITRO.1](#).):

- Patients who discontinue from the study during the lead-in period (prior to randomization), only need to complete an early discontinuation visit.
- Patients who discontinue from IP early will be encouraged to remain in the study and complete all remaining visits per the Schedule of Activities, including Visit 801.
- Patients who discontinue from the study early (regardless of whether they discontinue IP at the same time or have discontinued IP at an earlier visit), should complete an early discontinuation visit followed by the safety follow-up visit as per the Schedule of Activities.
- Patients who finish Visit 13 without early discontinuation of IP should complete a safety follow-up visit (Visit 801) 4 weeks after Visit 13.

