8.1.2. Temporary Discontinuation from Study Treatment

Patients can have temporary discontinuation of IP for up to a total of 14 days (consecutive or nonconsecutive).

In the event of a pump failure, MDI therapy is allowed for \leq 14 days. Bolus and basal insulin will be determined by the investigator or other HCP. When possible, continuing on IP is preferred. Investigational product may be withdrawn from the vial and injected as needed to cover meals and correct hyperglycemia using the insulin syringes provided.

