9.1.4.7. Mixed Meal Tolerance Test

A 4-hour MMTT will be performed in all patients at

- baseline (Week 0, Visit 4) and
- the end of the treatment period (Week 16, Visit 13).

The MMTT can

- occur 0 to 4 days prior to Visit 4 or Visit 13, but as close to the Visit date as possible.
- be rescheduled up to 2 times within the visit window, ideally at 24-hour intervals, if the patient does not meet the target FBG.
- occur after a non-severe hypoglycemic episode is recorded within the 8-hour fasting period and up to 2 hours prior to the test meal if it is treated and resolved with 20 grams or less of carbohydrate

The MMTT cannot occur

- if a correction bolus dose was given less than 4 hours before the start of the test meal.
- if non-severe hypoglycemic episode during the 8-hour fasting period and up to 2 hours prior to the start of test meal requires more than 20 grams of carbohydrate, or
- if patient has an episode of severe hypoglycemia within the past 24 hrs.

The day prior to the MMTT, patients will be instructed to

- follow normal eating and exercise routines
- refrain from intake of alcohol

The evening prior to the MMTT, patients will be instructed to

- fast for at least 8 hours prior to scheduled testing
- fill a new pump reservoir and infusion set
 - with open-label Humalog - Visit 4
 - with IP - Visit 13
- insert a new infusion set into an appropriate site

The morning of scheduled MMTT, patients will be instructed to

- measure SMBG at 4 AM
 - This SMBG value should be used by patients to evaluate the need for a correction bolus or the intake of no more than 20 grams of carbohydrate to arrive at the investigator site with a BG between 71 and 180 mg/dL prior to the MMTT.
- keep programmed basal rates
- continue to wear the CGM device until the end of the MMTT

- if the sensor session is scheduled to end on the day of the MMTT, the patient should end the sensor session and insert a new sensor the evening prior to the scheduled time of the MMTT.

Target FBG

Patients should have a FBG in the range of 71 to 180 mg/dL (4.0 to 10.0 mmol/L) prior to starting the MMTT.

Test Meal

- The test meal (approximately 700 kcal and 100 grams of carbohydrate) will consist of 2 cans of Ensure Plus®, Abbott Nutrition.
- Patients are expected to consume the meal within 15 minutes.
- Patients should consume the same test meal for both the baseline and end of primary treatment period MMTT.

Insulin Infusion

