The morning meal CR will be used to calculate the bolus dose for the MMTT, adjusting if needed for the fat content of the test meal. A supplemental correction dose based on the patient's ISF may be added to the bolus if the glucose is above the fasting or pre-meal target.

All patients will have a bolus dose given 0 to 2 minutes prior to the start of the meal.

- With open-label Humalog - Visit 4
- With IP - Visit 13

Sample Collection

Time 0 of the MMTT will be when the patient starts to consume the meal. Serial venous blood samples to measure serum glucose will be taken at time -15, 0, 15, 30, 60, 120, 180, and 240 minutes after the start of the meal.

Hypoglycemia during the MMTT

If the patient	Then the patient should
has signs or symptoms of hypoglycemia during the MMTT	have BG measured with the site-provided Point of Care BG meter.
has BG \leq 70 mg/dL (3.9 mmol/L)	receive 15 g of rapidly absorbable oral carbohydrate and repeat BG testing after 15 min or as clinically indicated.
has a repeated BG that is still \leq 70 mg/dL (3.9 mmol/L)	receive another 15 g of carbohydrate until BG is $>$ 70 mg/dL (3.9 mmol/L).
reaches a BG $>$ 70 mg/dL (3.9 mmol/L)	continue the sample collection of the MMTT per the schedule

Abbreviations: BG = blood glucose; MMTT = mixed meal tolerance test.

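### SAP Appendix 2 limits every CGM derivation to on-IP readings, so the ITT time-in-range analyses (H5, H6) would, as written, reuse the efficacy-estimand data

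*Protocol*

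**What the plan says.** **Estimands.** SAP 6.3 applies two estimands to the primary and multiplicity-adjusted objectives. ITT takes all data through Week 16 regardless of IP use. The efficacy estimand stops at permanent IP discontinuation. For the CGM endpoints, 6.3 attaches the further exclusion of temporary off-pump and off-treatment data to the efficacy estimand. SAP 6.11.2 sets 5% alpha for each estimand.

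**CGM (H5 24-hour and H6 daytime time in range).** Protocol 9.1.4.6 has all patients wear the blinded device for 14 days before Visits 4, 10 and 13. SAP 6.13 opens with the efficacy estimand, adds an ITT analysis of these two endpoints for the FDA, and sends the reader to Appendix 2 for derivations. The general specifications there keep only readings from valid days between first and last dose of study drug and remove temporary off-pump or off-treatment readings. No estimand is named.

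**MMTT (H2 1-hour and H3 2-hour PPG).** Protocol 8.1 says: "For patients who remain in the study after early discontinuation of IP, both efficacy (HbA1c) and safety data will be collected at scheduled visits". Protocol 9.1.4.7 states "A 4-hour MMTT will be performed in all patients at" baseline and Week 16, and gives the bolus insulin at the second test as "With IP - Visit 13"; the reservoir instruction for the evening before is the same. Protocol 7.2.1.5 says "Patients will give their last bolus dose of study insulin (LY900014 or Humalog) at Visit 13 with the MMTT or at early discontinuation", and under 7.8.2, once IP has stopped, "randomized patients should restart the rapid-acting analog insulin used prior to study entry". Protocol 5.3.1 says: "Patients who discontinue from IP early will be encouraged to remain in the study and complete all remaining visits per the Schedule of Activities". SAP Table ITRO 6.2 takes ITT PPG from Visit 13 whatever the IP use.

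**The concern.** H5 and H6 are alpha-controlled, and the SAP revision history records that ITT analyses of these CGM endpoints were deliberately added. An ITT analysis differs from an efficacy-estimand analysis only through the off-IP data that it admits. If the derivation step has already removed those data, the two analyses share one data set, and the ITT result tells the FDA nothing that the efficacy result does not.

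The MMTT text raises a smaller version of the same question. A site that looks up Protocol 8.1 when a patient stops IP finds HbA1c and no mention of the meal test. A site that looks up 9.1.4.7 finds an insulin instruction which that patient cannot follow. Some sites might then skip the test. A missing Week 16 PPG has no stated remedy: there is no earlier post-baseline MMTT for LOCF to carry forward, and the ITT imputation is described only for HbA1c.

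**Working it through.** **Design inputs.** The plan's own figures reproduce. The standard error is 0.88 × √(2/184) = 0.0917. Power is Φ(0.4/0.0917 − 1.96) = 99.2% (stated: at least 99%) and Φ(0.3/0.0917 − 1.96) = 90.5% (stated: 90%). Randomised number: 368/0.88 = 418.2, so 419 (stated: about 420). None of these figures changes.

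**The CGM rules side by side.**

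| Place | Data admitted | Estimand named |
|---|---|---|
| SAP 6.1, CGM data on IP | First to last treatment dose, less temporary off-pump or off-IP data | None needed: it defines on-IP data |
| SAP 6.3 | All data through Week 16; temporary-off exclusion attached to one estimand | ITT; efficacy |
| SAP 6.13 | First to last dose, less temporary-off data; then ITT added | Efficacy; ITT |
| SAP Appendix 2 | First to last dose, less temporary-off data | None |

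After randomisation, the Appendix 2 window is the 6.1 on-IP window. A program written from Appendix 2 gives one set of time-in-range values for both estimands.

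**Size, with assumed inputs.** Let r be the share of 368 patients with Week 16 data who are off IP, and m the share of those whose Week 16 value is lost. Suppose off-IP patients show no treatment difference and the on-IP difference is d. The complete ITT difference is (1 − r)d. The analysed difference is d(1 − r)/(1 − rm). The relative overstatement is 1/(1 − rm) − 1. Under the literal Appendix 2 rule m = 100% for patients who have permanently stopped. For the MMTT, m is unknown.

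| r | Off-IP patients, 368r | CGM, literal rule (m = 100%) | MMTT, m = 25% | MMTT, m = 50% |
|---|---|---|---|---|
| 1% | 3.7 | 1.0% | 0.3% | 0.5% |
| 2% | 7.4 | 2.0% | 0.5% | 1.0% |
| 5% | 18.4 | 5.3% | 1.3% | 2.6% |

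Power: assume 90% for the on-IP comparison and equal SDs. Complete ITT data multiply the noncentrality by √(1 − r), giving 89.7%, 89.4% and 88.5%. The literal CGM rule leaves it at 90%. For the MMTT at m = 50% the factor is √((1 − r)/(1 − rm)), giving 89.9%, 89.7% and 89.2%. When d = 0 both differences are zero, so this mechanism creates no false positive.

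If off-IP shares differ by arm (rL, rH) and off-IP PPG lies g away from on-IP PPG in both arms, the omitted shift is g(rL − rH) − g[rL(1 − m)/(1 − rL·m) − rH(1 − m)/(1 − rH·m)]. With 2% v 1% and g = 10 mg/dL it is 0.05 mg/dL at m = 50%. With 5% v 2% and g = 40 mg/dL it is 0.58 mg/dL.

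**Temporary stops.** Protocol 8.1.2 allows 14 days off IP in total, as long as one CGM session. A valid day needs 0.70 × 288 = 201.6, so 202 readings, and at most 86 may be absent: 86 × 5 minutes = 7.2 hours. If off-IP readings are removed before this check, a longer break removes the whole day. The SAP does not state the order.

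**The case against.** On CGM, the best defence is that Appendix 2 was meant for the efficacy estimand. It nearly repeats the opening of SAP 6.13, which has that scope, and refers back to that section. SAP 6.3 restricts the temporary-off exclusion in the same way. The CGM row of Table ITRO 6.2 carries no IP limit, whereas the insulin-dose, SMBG and 1,5-AG rows do. Reading Appendix 2 to cancel the added ITT analysis would defeat the purpose of adding it. This is a plausible account of intent. It does not remove the defect: the rule sits under general specifications, 6.13 delegates derivation to it, and nothing in it says it is limited to one estimand.

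On the MMTT, the objection largely succeeds. A reader might infer from Protocol 8.1 that off-IP meal tests are not collected and that the ITT analyses of H2 and H3 therefore lack data. The documents do not support that. Section 8.1 does not say that HbA1c is the sole efficacy measure. Section 5.3.1 keeps these patients on the full schedule, 8.1.1 sends them to it for follow-up procedures, and 9.1.4.7 covers all patients. SAP 6.1 has a date rule separating on-IP from off-IP MMTTs, which presupposes that the latter exist. Nor is the protocol silent on their insulin: 7.8.2 names the pre-study analog. What remains is narrower wording in 8.1 and an instruction in 9.1.4.7 that off-IP patients cannot follow as written.

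**Conclusion.** The CGM point holds. As written, Appendix 2 gives the ITT analyses of H5 and H6 the on-IP data set, contrary to SAP 6.3 and to the purpose of the ITT analysis in 6.13. The MMTT point holds only as a lesser wording conflict affecting H2 and H3.

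The effect is likely small and cannot be calculated from the documents. The ranges shown rest on assumed values of r and m, on no treatment difference off IP and, in the differential case, on assumed PPG gaps. The CGM column is also a simplification, because the MMRM uses Visit 10 as well.

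A reader might take the 12% dropout allowance, or the 420 − 368 = 52 patients behind it, as the affected share. It does not measure that share: Protocol 10.1 treats the 368 as completing the study, while 5.2 says "526 participants will be screened to achieve 420 randomized and 368 patients completing 16 weeks of treatment". Neither count tells how many patients stop IP and stay. Nor does the point reach the primary objective or HbA1c superiority (H1, H4), since off-IP HbA1c is expressly collected and has its own ITT analysis.

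**What to change.** 1. In SAP Appendix 2, limit the first-to-last-dose rule and the temporary off-pump/off-treatment exclusion to the efficacy estimand. State that ITT time in range uses all valid CGM days through Week 16 regardless of IP use.
2. In Protocol 8.1, list the Visit 13 MMTT and the blinded CGM sessions beside HbA1c as efficacy data collected after IP is stopped.
3. In Protocol 9.1.4.7, cross-refer to 7.8.2 so that patients who have permanently stopped IP do the Visit 13 test with their restarted pre-study analog.

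The first change is one SAP sentence plus a second time-in-range derivation for H5 and H6. The other two are wording changes that a site memo can carry. No procedure is added, because the MMTT and CGM sessions are already scheduled for all patients. The cost is a small burden on patients who have stopped IP and might otherwise not have been asked to do them.
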